#### **4.7 Exploratory Aim 1: TranS-C Treatment Condition on Credibility and PhenX Toolkit**

MLM will be used to test TranS-C treatment condition (Adapted vs. Standard TranS-C) predicting PhenX Toolkit outcomes of substance use and suicidality at post-treatment and 6FU. The approach to MLM will mirror Aim 2, except the outcomes will be substance use and suicidality from the PhenX Toolkit. Linear regression will be used to test treatment condition (Adapted vs. Standard TranS-C) predicting patient perceptions of TranS-C's credibility at post-treatment.

#### **4.8 Exploratory Aim 2: Treatment Effects Moderated by Risk Factors**

Using MLM, three-way interactions between treatment condition (Adapted or Standard TranS-C versus UC-DT), time, and risk factors will be used to evaluate moderators of patient outcome (i.e., sleep and circadian problems, functional impairment, and psychiatric symptoms). Each moderator and outcome will be tested in a separate model. Moderators will include age, sex, and sleep/circadian and psychiatric symptoms at baseline. The level 1 equation will include the moderator and dummy-coded time indicators as the predictors (0 = pre-treatment, 1 = post-treatment). The level 2 equation will include dummy-coded treatment condition (0 = UC-DT, 1 = Adapted or Standard TranS-C), treatment by time by moderator interaction terms, and dummy-coded counties (0 = Alameda, 1 = Contra Costa, 2 = Kings, 3 = Monterey, 4 = Placer, 5 = Santa Cruz, 6 = Solano, 7 = Santa Clara, 8 = Santa Barbara, and 9 = Lake) as predictors. A significant interaction indicates a moderating effect and will be probed with planned contrasts (e.g., moderating effects on the differences between treatments in change from pre-treatment to post-treatment) and graphs. Simple slope analyses will be conducted for significant continuous moderators.

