**Table 1. SPIRIT Depiction of Timing and Measures Collected for Implementation Phase**

[figure not shown]
	Screening	Post-Training	Pre-Treatment	Mid-Treatment	Post-Treatment	6-Months Post-Treatment
Patient						
Sociodemographics			X		X	X
Eligibility Items	X					
PROMIS-SD P	X		X	X	X	X
PROMIS-SRI			X	X	X	X
DSM-5 Cross-Cutting			X		X	X
SDS			X		X	X
Sleep Health Composite			X	X	X	X
PHENX Toolkit			X		X	X
CEQ					X	
Provider						
Sociodemographics		X				
Occupation		X				
Acceptability P		X		X	X	
Appropriateness		X		X	X	
Feasibility		X		X	X	
Number of Sessions					X	

*Note.* Allocation to Adapted or Standard TranS-C occurs at the county level and prior to enrollment of any participants in that county (i.e., patients or providers). Enrollment of patients and allocation to immediate TranS-C or delayed TranS-C (UC-DT) occur after the screening and before the pre-treatment assessment. Enrollment of providers after the training. P = Primary Outcome. PROMIS-SD = PROMIS-Sleep Disturbance; note: PROMIS-SD is only assessed during the pre-treatment assessment if done more than one month after the screening to minimize burden for patients. PROMIS-SRI = PROMIS-Sleep Related Impairment. SDS = Sheehan Disability Scale. CEQ = Credibility/Expectancy Questionnaire

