### 3.5.2.2 Secondary Outcomes

*Sleep-Related Impairment.* The 16-item PROMIS-Sleep Related Impairment (PROMIS-SRI) assesses daytime impairment related to sleep problems over the past seven days on a scale from 1 (not at all/never) to 5 (very much/always) [62]. Scores range from 16-80, with higher scores indicating greater impairment (e.g., daytime sleepiness, difficulty concentrating). This measure has demonstrated excellent psychometric properties [61, 62].

*Functional Impairment.* Functional impairment is assessed via the Sheehan Disability Scale (SDS) [76]. Impairment in work and school, social life, and home and family is rated on a scale from 0 (not at all) to 10 (extremely). Scores range from 0-30, with higher scores indicating greater impairment. This measure has demonstrated good reliability and validity [76, 77].

*Overall Sleep Health.* The Sleep Health Composite is proposed to capture overall sleep health for the complexity of sleep problems in SMI that are covered by TranS-C [78]. It is defined as the sum of scores on six sleep health dimensions (each dimension dichotomized as 1 = good; 0 = poor): Regularity (midpoint fluctuation), Timing (mean midpoint), Efficiency (sleep efficiency), Duration (total sleep time), Satisfaction (sleep quality question on PROMIS-SD), and Alertness (daytime sleepiness question on PROMIS-SRI). All dimensions – except Satisfaction and Alertness – are assessed via questions about sleep-wake patterns over the past seven days (e.g., *In the past week, what time have you usually woken up in the morning?*). Scores range from 0-6, with higher scores indicating better sleep health. Initial validity of this measure has been established [78].

*Psychiatric Symptoms.* The DSM-5 Cross-Cutting Measure assesses psychiatric symptoms across 13 mental health domains. Participants rate how often they were bothered by each symptom on a scale from 0 (not at all) to 4 (nearly every day). Scores range from 0-52, with higher scores indicating more severe symptoms. This measure has demonstrated good test-retest reliability and clinical utility [79, 80].

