### 3.8 Sample Size

Sample size was determined via power analyses with Optimal Design [85, 86] and Stata 15 [87] and a two-sided alpha of 0.05. We used the original  $N = 8$  counties that agreed to participate, though as noted above, new counties have since been recruited to meet sample size goals determined by the following calculations. For Aims 1 and 3, 60 patients from eight randomized clusters/CMHCs was found to provide over 90% power to detect large effects (average  $d=0.89$  from [35]) between TranS-C and UC-DT, and over 80% power to detect a medium effect ( $d=0.50$ ) between Standard and Adapted TranS-C. For Aim 2, based on a prior study with a similar aim/measure [88], we expected a large effect size ( $d=0.80$ ) between Standard and Adapted TranS-C on the primary outcome of acceptability. Prior studies have reported high correlation coefficients between acceptability, feasibility, and appropriateness ( $rs=.67-.90$ ) [75, 89], thus the analysis for acceptability was expected to sufficiently power the other outcomes. Based on the site intra-class correlation (ICC) estimated from similar prior studies [90, 91], we assumed the ICC to be 0.01 and the inflation factor was calculated as  $1+(n-1)\times ICC$ . Eight clusters with an average cluster size of 10 was found to be needed to achieve over 80% power to detect a large effect for the outcome (acceptability) at the provider level. Thus, to test this aim, we would need at least 80 CMHC providers: 10 providers from 8 CMHCs (at least 4 CMHCs per randomized arm).

In sum, we aimed to randomize at least eight CMHC clinics to either Standard or Adapted TranS-C, with at least 80 providers (10 per CMHC). The goal for patients is 240 patients (30 per CMHC) randomized to immediate Standard or Adapted TranS-C and 240 randomized to UC-DT (30 per CMHC). Adding 20% to account for attrition, the total target sample size for providers is 96 and for patients is 576.

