## 4 PLANNED ANALYSES

### 4.1 Preliminary Analyses and Missing Data

Analyses will use all available data (intent-to-treat) [93]. If dropout is related to other variables, they will be included as predictors. Baseline between-group differences on demographic variables will be examined. These tests will not be used to select covariates in the primary intention-to-treat analysis [94-97]. Instead, covariates will be carefully selected at the conclusion of the trial—given the variations due to COVID-19 and the CMHC context (see Discussion)—and the potential influences of baseline differences will be evaluated as moderators (approach to moderation described below). Analyses comparing TranS-C to UC-DT will evaluate change in outcomes from pre-treatment to post-treatment. Analyses comparing Adapted to Standard TranS-C will evaluate change in outcomes from pre-treatment to post-treatment and pre-treatment to 6FU (see Method and Discussion for more details).

Distributions will be evaluated to detect outliers, and we will ensure that assumptions of planned analyses are met. Covariates will include the patient variables for which we stratified (i.e., age and presence of psychosis or substance use). For all statistical models, counties will be entered as dummy variables rather than a level of analysis due to the relatively small number of clusters. The average intraclass correlation on provider and patient level outcomes will be reported. The Benjamini–Hochberg procedure [98] will be used to correct for multiple testing for confirmatory analyses on the primary outcomes (i.e., sleep disturbance and acceptability) [99].

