### 4.3 Aim 1: Effectiveness Outcomes of Standard or Adapted TranS-C versus UC-DT

Multilevel modeling (MLM) [100-102] will be used to account for multiple observations nested within

patient. The level 1 equation will include dummy-coded time indicators as the predictor (0 = pretreatment, 1 = post-treatment). The level 2 equation will include dummy-coded treatment condition (0 = UC-DT, 1 = Adapted or Standard TranS-C), treatment by time interaction terms, and dummy-coded counties (0 = Alameda, 1 = Contra Costa, 2 = Kings, 3 = Monterey, 4 = Placer, 5 = Santa Cruz, 6 = Solano, 7 = Santa Clara, 8 = Santa Barbara, and 9 = Lake) as predictors. The treatment effects of interest will be significant treatment by time interactions at the 5% level on the primary outcome of sleep disturbance and the secondary outcomes of sleep-related impairment, functional impairment, and psychiatric symptoms, all modeled as continuous variables. Significant treatment by time interactions indicate that change in patient outcomes is significantly different comparing Adapted or Standard TranS-C to UC-DT. Significant interactions will be interpreted using planned contrasts (i.e., treatment effects on change from pre-treatment to post-treatment) and graphs. Additionally, the indirect effects of TranS-C relative to UC-DT on functional impairment and psychiatric symptoms through improvements in sleep disturbance and sleep-related impairment will be tested using multilevel structural equation modeling [103].

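### In the Section 4.8 models where the moderator is the outcome's own baseline score, missing post-treatment scores make the standard error of the moderation test too small

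*Combined protocol and SAP*

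**What the plan says.** Section 4.8 looks for "moderators of patient outcome (i.e., sleep and circadian problems, functional impairment, and psychiatric symptoms"). It crosses moderators and outcomes without excluding any pair: "Each moderator and outcome will be tested in a separate model. Moderators will include age, sex, and sleep/circadian and psychiatric symptoms at baseline". On the form of the model it says: "The level 1 equation will include the moderator and dummy-coded time indicators as the predictors (0 = pre-treatment, 1 = post-treatment"). The test is the three-way interaction of treatment, time and moderator. A significant result is read as moderation and followed by contrasts and, for continuous moderators, simple slopes.

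Four other places bear on this:

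- Section 3.5.2.2 lists one psychiatric symptom scale: "The DSM-5 Cross-Cutting Measure assesses psychiatric symptoms across 13 mental health domains". Sleep is measured by PROMIS-SD, PROMIS-SRI and the Sleep Health Composite, and Section 4.8 does not say which of these is the sleep/circadian moderator.
- Section 4.3 says that multilevel modeling "will be used to account for multiple observations nested within" patient. Neither it nor Section 4.8 gives a random-effect or residual structure.
- Section 4.1 says: "Analyses will use all available data (intent-to-treat"). A patient with only a pre-treatment score therefore stays in the model.
- Section 3.8 says: "Adding 20% to account for attrition, the total target sample size for providers is 96 and for patients is 576".

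**The concern.** When the moderator is the baseline value of the outcome being modeled, the same number stands on both sides of the equation at time 0. Those rows carry no error, yet the model counts them when it estimates a single residual variance. If every patient also has a post-treatment row, this does no harm. If some patients have only the error-free row, the model treats the interaction as better estimated than it is.

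At stake is whether patients with worse symptoms at baseline gain more or less from TranS-C. For own-scale pairs the false-positive rate would exceed the nominal level, and intervals for the moderation effect would be too narrow. The Benjamini–Hochberg correction in Section 4.1 covers only confirmatory analyses of the primary outcomes, so nothing offsets the excess.

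**Working it through.** **The plan's own figures.** 480 × 1.20 = 576, as Section 3.8 states. If 480 of 576 patients supply a post score, retention is 480/576 = 0.833, a loss of 16.7%. If the 20% is read as the share lost, retention is 0.80. The plan gives no power or error figure for the moderator tests, so there is no further figure to reproduce. The two-sided 5% level is taken from Section 3.8; Section 4.8 states none.

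**Assumptions.** Random intercept, one residual variance for both times, model-based standard errors, all lower-order terms included, no true moderation, and a pre-post correlation of 0.5 (0.3 and 0.7 also tried). Losses of 30% and 40% are hypothetical.

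**Algebra.** Let n0 patients have a pre-treatment row and n1 of them a post row, and let the moderator M be the pre-treatment score.

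1. At time 0 the outcome equals M, so the fit is essentially exact. Post residuals then share nothing with pre residuals, and the between-patient variance is estimated at or near zero.
2. If v is the true residual variance at post, the pooled estimate is about v × n1/(n0 + n1), because only the n1 post rows carry error.
3. The three-way coefficient is the post treatment × M slope minus the pre slope. The model gives it variance (pooled variance) × c × (1/n1 + 1/n0), where c depends on the spread of treatment × M. Substituting: v × n1/(n0 + n1) × c × (n0 + n1)/(n0 × n1) = v × c/n0.
4. The pre slope is known without error, so the true variance is v × c/n1.
5. The ratio of model SE to true SE is therefore √(n1/n0) = √retention. The model behaves as if every enrolled patient had a post score. The type I error is 2 × [1 − Φ(1.96 × √retention)].

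**Results.** The simulation used N = 576, county dummies, three stratification covariates and 3,000 runs per setting. Simulation error is about 0.4 points near 5%.

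| Post scores missing | SE ratio | Type I error, formula | Simulation | Repeat simulations |
|---|---|---|---|---|
| 0% | 1.000 | 5.0% | 5.8% | 4.4–5.7% |
| 16.7% | 0.913 | 7.4% | 7.0% | 7.5–8.3% |
| 20% | 0.894 | 8.0% | 8.8% | 7.8–8.5% |
| 30% (hypothetical) | 0.837 | 10.1% | 10.1% | 10.2–10.4% |
| 40% (hypothetical) | 0.775 | 12.9% | 13.5% | 12.2–13.6% |

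A packaged mixed-model routine gave SE ratios of 1.000, 0.894 and 0.776 at 0%, 20% and 40% missing, with boundary warnings. The mean estimate stayed within 0.004 of zero.

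**Variations at 20% missing.** Type I error was 8.5% with correlation 0.3, 7.2% with correlation 0.7, 9.2% when dropout depended on baseline, and 8.3% when counties differed in change.

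**Comparators.** A symptom moderator on a different scale from the outcome gave 5.3% at 20% missing and 5.9% at 40%. Regressing the post score on treatment, baseline, their product, county and covariates gave 4.6–5.8% across 0–40% missing. The multilevel model restricted to patients with both scores also stayed at about 5%.

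**The case against.** The strongest reply is that the plan does not state the model simulated here. It says only that multilevel modeling is used, so the size of the effect depends on an assumed random intercept and common residual variance. That stands, and the result is conditional on it. A separate residual variance at each time is no remedy, however: the time-0 variance can go to zero and the likelihood becomes degenerate. An analyst would probably see a boundary warning, but the plan does not say what to do then.

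Scope is limited too. Section 4.8 names constructs rather than scales. With 4 moderators and 3 outcomes, 2 of 12 models are own-scale; with every sleep scale on both sides, 4 of 30 are. At 16.7% loss the excess is 2.4 points per test, so 2 × 0.024 ≈ 0.05 to 4 × 0.024 ≈ 0.10 extra expected false positives. The uncorrected tests already carry 12 × 0.05 = 0.6 to 30 × 0.05 = 1.5.

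A reader might infer four stronger things that the documents do not support:

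- *That false moderators will be declared, or that all symptom moderators are affected.* The estimate is unbiased, the excess is a few points, and different-scale pairs stay near nominal.
- *That error rates of 10–13% are to be expected.* The only attrition figure is the 20% addition in Section 3.8. The Discussion reports turnover among providers and patients but gives no rate of missing post scores.
- *That PROMIS-SD is certainly an own-scale pair.* The sleep moderator is not named. Table 1 also notes that "PROMIS-SD is only assessed during the pre-treatment assessment if done more than one month after the screening"; where both scores exist and the screening score were the moderator, exact identity would fail for those patients.
- *That the time × moderator term is left out.* Section 4.8 does not list it, and leaving it out would be far worse (simulated false-positive rate 100%, bias about −0.33). But the text does not say that lower-order terms are excluded, so this only needs stating.

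Nor do the documents rank the symptom moderators above age or sex.

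**Conclusion.** The concern holds for own-scale pairs. At least one follows from the plan as written, because the psychiatric moderator and the psychiatric outcome share the only listed scale, and the all-available-data rule keeps the baseline-only rows. The direction is always towards too small a standard error. At the attrition that the plan itself allows for, the size is modest: about 7–8% in place of 5%. The harm comes only from patients without a post score.

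This rests on the assumed covariance structure, on model-based standard errors, and on the moderator being the same score as the time-0 outcome. The Aim 1 treatment effects, Aims 2 and 3, and the primary conclusions are untouched. It is worth correcting because the error is systematic and the correction loses no information on the term tested.

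**What to change.** In Section 4.8, add that whenever the moderator is the baseline value of the outcome being tested, the test is the treatment × baseline term in a regression of the post-treatment score (post-delay score for UC-DT) on treatment, baseline score, their product, county and the stratification factors. An equivalent option, which keeps one model form throughout, is to restrict the multilevel model to patients with both scores and state that all lower-order terms are included. Keep the planned model for all other pairs.

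In the same edit, name the scale used for each symptom moderator, say whether screening or pre-treatment PROMIS-SD is the baseline, and state the random-effect and residual structure.

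The cost is a few sentences and no new data. Patients without a post score contribute nothing to this term under either model.

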## 3.5.2 Patients

### 3.5.2.1 Primary Outcomes

*Sleep Disturbance.* The 8-item PROMIS-Sleep Disturbance (PROMIS-SD) assesses disruption to sleep (e.g., restlessness, trouble staying asleep) over the past seven days [62]. Items are rated on a scale from 1 (not at all/never/very poor) to 5 (very much/always/very good), and scores range from 8-40, with higher scores indicating greater disturbance. This measure has demonstrated acceptable reliability and validity [61, 62].

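### The moderator model listed in section 4.8 has a three-way term but no two-way interactions, so a uniform treatment effect, or regression to the mean, can test as moderation

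*Combined protocol and SAP*

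**What the plan says.** Section 4.8 (Exploratory Aim 2) compares TranS-C with UC-DT and fits a separate model for each moderator and outcome. On the moderators: "Moderators will include age, sex, and sleep/circadian and psychiatric symptoms at baseline". The outcomes are sleep and circadian problems, functional impairment and psychiatric symptoms.

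- Level 1: "The level 1 equation will include the moderator and dummy-coded time indicators as the predictors".
- Level 2: treatment, then "treatment by time by moderator interaction terms, and dummy-coded counties".
- Decision rule: "A significant interaction indicates a moderating effect and will be probed with planned contrasts".

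Section 4.8 names no treatment x time, treatment x moderator or time x moderator term. It does not say whether continuous moderators are centred or how sex is coded. The Aim 1 model in section 4.3 lists "treatment by time interaction terms, and dummy-coded counties".

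Section 4.1 sends further variables down the same route: "the potential influences of baseline differences will be evaluated as moderators", using the moderation approach of section 4.8.

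**The concern.** A three-way coefficient measures moderation only if the lower-order interactions are also in the model. Without treatment x time, the treatment difference in change is forced to zero where the moderator equals zero. A treatment effect that is the same for everyone can then enter only through the three-way product. Without time x moderator, any relation between the moderator and change that both arms share has to be absorbed in the same place.

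Some raw scales cannot reach zero. Patients are 18 or older, and for PROMIS-SD "scores range from 8-40, with higher scores indicating greater disturbance". For the DSM-5 Cross-Cutting Measure zero is possible but is the lowest score: "Scores range from 0-52, with higher scores indicating more severe symptoms".

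The risk is a set of false subgroup claims about who benefits from TranS-C. The planned contrasts and simple slopes would not expose them if they come from the same constrained model.

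**Working it through.** **The two models.** Let t = 0/1 for pre/post, T = 0/1 for UC-DT/TranS-C, and M the moderator. County dummies and a patient intercept are in both.

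- Listed: Y = b0 + b1·t + b2·M + b3·T + b4·T·t·M. Treatment difference in change = b4·M.
- Full: the same, plus b5·T·t + b6·t·M + b7·T·M. Treatment difference in change = b5 + b4·M.

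If the effect is a uniform -d, the truth is b5 = -d and b4 = 0. The listed model has no b5, so b4·M must approximate -d.

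**Inputs from the plan.** Section 3.8 gives 240 patients per arm, two-sided alpha 0.05 and an expected d=0.89 for TranS-C against UC-DT. Its total reproduces: (240 + 240) x 1.20 = 576. Section 4.8 gives no power, sample size or effect size of its own, so there is no figure there to reproduce. The simulation uses the 480 evaluable patients and ten counties.

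**Assumptions not in the plan.** Pre-post correlation 0.5; a change of -0.3 SD in both arms; sex 50/50; age mean 45, SD 13; DSM-5 score mean 20, SD 10; PROMIS-SD mean 28, SD 6. Sex, age and DSM-5 score are generated independently of the outcome. The DSM-5 rows therefore describe that score as moderator of a different, uncorrelated outcome.

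**Method.** 400 simulated trials per cell, random-intercept model by REML, 5% two-sided test of b4, true moderation zero throughout. The Monte Carlo standard error at 5% is sqrt(0.05 x 0.95 / 400) = 1.1 percentage points.

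**False-moderation rate (%)**

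| Moderator and coding | d=0 | d=0.2 | d=0.5 | d=0.89 |
|---|---|---|---|---|
| Listed: sex 0/1 | 7.0 | 21.0 | 82.5 | 99.8 |
| Listed: age in years | 5.3 | 54.3 | 100 | 100 |
| Listed: DSM-5 raw | 5.5 | 40.3 | 99.3 | 100 |
| Listed: sex +/-0.5 | 6.3 | 4.3 | 4.3 | 4.0 |
| Listed: age centred | 5.5 | 5.0 | 4.8 | 3.8 |
| Listed: DSM-5 centred | 6.0 | 5.3 | 5.5 | 3.3 |
| Listed: baseline PROMIS-SD as moderator of itself, raw | 63.8 | 98.5 | 100 | 100 |
| Listed: the same, centred | 100 | 100 | 100 | 100 |
| Full model, range over all eight codings | 3.5-7.5 | 3.8-8.0 | 3.5-6.3 | 3.8-7.8 |

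A separate run of the listed model gave 84% (sex 0/1) and 99.5% (age in years) at d=0.5. For baseline PROMIS-SD at d=0 it gave 60% raw and 100% centred. Its full model gave about 3-7%.

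**What the false result looks like.** At d=0.5 the mean b4 for 0/1 sex is -0.30. The model reports an effect of -0.30 in one sex and exactly zero in the other, when the truth is -0.5 in both. For age, b4 averages -0.0094 per year, and -0.0094 x 45 = -0.42 at the mean age. Most of the uniform effect has become an apparent age gradient.

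**Why centring does not help for the outcome's own baseline.** With pre-post correlation 0.5, change regresses on baseline with slope 0.5 - 1 = -0.5 SD per SD, or about -0.5/6 = -0.083 SD per PROMIS-SD point, equally in both arms. The listed model lets change vary with M only in the treated arm, through b4. After centring, b4 averages about -0.054 per point at d=0, although the arms do not differ. Adding treatment x time alone would leave this problem in place, because the missing term is time x moderator.

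**The case against.** **The authors may intend the full model.** The term lists are not exhaustive: section 4.1 promises the stratification variables as covariates, yet the lists in sections 4.3, 4.4 and 4.8 do not show them. The planned simple slopes make little sense if the treatment effect must vanish at age 0. In two-level notation, a treatment predictor acting on the time slope would ordinarily generate the cross-level two-way terms. This is a fair reading, and it means the plan does not establish which model will be fitted. But the text does not say that lower-order terms are included, and an analyst who follows the list gets a wrong test.

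**Aim 1 proves nothing about convention.** A reader might infer that, because section 4.3 lists treatment x time, its absence from section 4.8 is deliberate. That does not follow. In section 4.3 it is the only interaction possible, so it cannot show how the plan treats lower-order terms. Equally, the plural in section 4.8 does not imply them, because section 4.3 uses the same plural for a single product.

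**Centring removes the problem for age, sex and an unrelated symptom score.** This stands: those rates are 3.3-6.3%. But section 4.8 does not mention centring, and centring does not rescue baseline sleep symptoms as moderator of a sleep outcome. That pairing falls within the stated moderators and outcomes.

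**Placing baseline moderators at level 1 is a further error.** A reader might press this. With fixed effects only, the level label does not change the combined model, so it is a labelling point.

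**Conclusion.** The point holds in conditional form. As listed, the section 4.8 model omits all two-way interactions.

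- For uncentred age, 0/1 sex or a raw symptom score, a uniform treatment effect is called moderation in about 21-54% of trials at d=0.2, 83-100% at d=0.5 and about 100% at the planned d=0.89.
- For the baseline value of the outcome, the rate is about 60-100% with no treatment effect at all, whatever the centring.
- With all two-way terms added, it is 3.5-8% throughout.

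A reader might go further and infer that any real treatment effect will be reported as moderation, or that nearly every moderator will test significant. The plan does not support that. Coding is unstated, centred or +/-0.5 coded age, sex and DSM-5 score stay near the nominal 5%, and at d=0.2 the uncentred rates for these three are well below 100%.

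Nor does the point reach the main result. The aim is exploratory, section 4.1 confines its multiplicity correction to confirmatory analyses of the primary outcomes, and the Aim 1 model contains treatment x time.

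The exact percentages rest on the assumed correlation, moderator distributions and independence stated above. The omission is in the text, and the direction of the error follows from the algebra.

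**What to change.** In section 4.8, state that each moderator model includes the main effects of treatment, time and moderator, all three two-way interactions (treatment x time, treatment x moderator, time x moderator) and the three-way term, and that moderation is judged on the three-way term alone. State that continuous moderators are centred, so that lower-order terms can be interpreted, and state how sex is coded. Apply the same specification to the baseline-difference moderators of section 4.1. Baseline moderators may be relabelled as level 2 for tidiness.

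The cost is a sentence or two in the plan, with no new data. Section 6 has assessments continuing after the date of this protocol version, so by its timetable the change could be made before final analysis. If the full model was always intended, the same text removes the ambiguity.
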